### 8.3.3 Vital Signs

Vital signs parameters include blood pressure, pulse rate, oral temperature and respiratory rates. Vital signs assessments will be performed at screening, baseline and Week 4, 8, 12, 16, 20, 24 and 28 visits.

Descriptive summaries (N, mean, median, standard deviation, minimum and maximum values) of observed values and change from baseline in each vital sign parameter at each assessment visit will be presented. A listing will be provided for the vital sign parameter assessments for all enrolled patients.

### 8.3.4 Physical Examination

Physical examination assessments will be performed at screening, baseline and Week 4, 8, 12, 16, 20, 24 and 28 visits. Physical examination results will be listed for all enrolled patients.

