### 2.3 DRUG PROFILE

Several research groups have developed or are attempting to develop dual PPAR $\alpha/\gamma$  agonist, some of which may eventually reach desirable clinical efficacy and safety end point. But if the agonist has higher PPAR $\gamma$  binding properties then several of the side effects such as edema, weight gain, bone effects and cardiovascular complications may occur. Therefore, there has been an increasing interest to develop new molecular entities which can treat insulin resistance, lower plasma glucose in diabetic patients and improve lipid profile without weight gain and cardiovascular risk.

Approved by: [name] [name] Protocol No.: SARO.17.010

CONFIDENTIAL PAGE 24 OF 80

If a new Chemical Entity (NCE) having a superior PPAR-α agonist activity with a moderate
PPAR- $\gamma$ agonist activity is developed, it may have a more desirable clinical profile with no
edema or weight gain effects.

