#### **6.1.2.2** Physical Examinations

Physical examination will be performed in accordance with the Schedule of Assessments (Table 1). The physical examination will consist of an evaluation of the head, neck, eyes, ears, nose, throat, chest, heart, lungs, abdomen, skin, extremities, and the neurological and musculoskeletal systems.

Patients' body weight will be recorded during all physical examinations. Height will be recorded at Screening Visit only.

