### 8.2.3 Safety Analysis

All safety analysis will be carried out on the safety population. The frequency tabulations of abnormal clinical laboratory values for the parameter will be presented by visit. All safety parameters (clinical laboratory testing, ECG, physical examination and vital signs) will be summarized using the following descriptive statistics: N, mean, median, standard deviation, minimum and maximum for continuous variables, and patient counts and percentages for categorical variables.

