#### 9.4.5 Expected Adverse Events

Adverse events reported by 2% or more patients treated with Saroglitazar magnesium during the double-blind, active-controlled study with pioglitazone as the comparator regardless of causality included gastritis and asthenia. In the double-blind placebo controlled study, AEs reported by 2% or more patients treated with Saroglitazar magnesium included gastritis, dyspepsia, pyrexia and pain. The details of AE(s) experienced during the Saroglitazar magnesium studies are mentioned in the IB. Principal Investigator(s) are advised to provide protocol education for patients and caregivers for potential symptoms of adverse effects that should be reported to the site/PI, such as skeletal muscle pain, weight gain, peripheral edema, shortness of breath, hypoglycaemia, etc.

CONFIDENTIAL
PAGE 71 OF 80

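### The SAP plans no summary of post-baseline body weight or weight change, although the protocol makes body weight a separate safety criterion

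*SAP*

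**What the plan says.** **Protocol.** Body weight is item 3 of the safety assessment in section 3.3, and the synopsis repeats it. It stands apart from vital signs (item 1) and physical examination (item 2). Section 6.1.2.2 states: "Patients' body weight will be recorded during all physical examinations". Section 7.2 has weight measured at screening and at every visit from Visit 2 to Visit 9. Section 9.4.5 advises investigators to teach patients about symptoms to report, including "skeletal muscle pain, weight gain, peripheral edema, shortness of breath, hypoglycaemia". On analysis, the synopsis (Statistical Methods, Safety Analysis) says that all collected safety data will be listed and, as appropriate, summarised. Section 8.2.3 says: "All safety parameters (clinical laboratory testing, ECG, physical examination and vital signs) will be summarized".

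**SAP.** Section 8.1 lists adverse events, vital signs, laboratory tests, ECG, echocardiogram and physical examination, with no body-weight item. Section 8.2 directs the descriptive safety assessment at the endpoints in that list. Section 8.3.3, which provides observed values and change from baseline by visit, defines its scope thus: "Vital signs parameters include blood pressure, pulse rate, oral temperature and respiratory rates". Section 8.3.4 says of physical examination: "Physical examination results will be listed for all enrolled patients". Weight appears by name only in section 5, among the demographic and baseline characteristics.

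**The concern.** Safety is the primary endpoint, and weight is one of the few safety measures taken at every clinic visit from Visit 2. Yet the plan provides a by-visit change summary for oral temperature and respiratory rate and none for weight.

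Two things would be lost. First, adverse-event tables do not replace a weight summary. Weight gain reaches them only when someone reports it and it is judged to be an adverse event, so a gain of a kilogram or two shared by most patients could go uncounted. Second, the trial has no control arm, and protocol 5.8 allows obesity to be managed by local standard of care throughout. Weight change is therefore an obvious competing explanation for changes in liver fat, adipose volume, lipids and insulin resistance, and a reader of the report will look for it. Whole-body MRI gives tissue volumes only at baseline and Week 24 and does not show the course of weight over visits.

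**Working it through.** The documents give no figure for this point, so there is none to reproduce. The check sets the protocol's commitments beside every SAP section that produces output.

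**Step 1. Where weight could appear in the SAP**

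| SAP section | Output planned | Body weight named? |
|---|---|---|
| 5, baseline characteristics | Summary at baseline | Yes, baseline only |
| 6.2 and 6.4, efficacy | Change summaries with 95% CI | No (adipose and muscle volume only) |
| 8.1, safety endpoints | List of endpoints | No |
| 8.3.2, adverse events | Counts and percentages by preferred term | Only if weight gain is reported as an event |
| 8.3.3, vital signs | Observed value and change by visit | No |
| 8.3.4, physical examination | Listing | No |
| 8.3.5 to 8.3.7, laboratory, ECG, echocardiogram | Summaries | No |

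No row gives an aggregate summary of weight after baseline.

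**Step 2. What links weight to the physical examination listing.** The link is an inference from protocol 6.1.2.2 ("body weight will be recorded during all physical examinations"). SAP 8.3.4 does not name weight, so even an individual listing of weights is likely rather than guaranteed.

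**Step 3. How many values are affected.** Protocol 7.2 gives nine weights per patient: screening, Visit 2 (baseline), and Visits 3 to 9 (Weeks 4, 8, 12, 16, 20, 24 and 28). Post-baseline weights per patient: 9 - 2 = 7. With 15 patients, the maximum is 15 x 7 = 105. Of these, 15 x 6 = 90 fall at Weeks 4 to 24 and 15 x 1 = 15 at the Week 28 follow-up.

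**Step 4. What a summary could show (illustration only).** The half-width of a 95% t-interval for mean change is t(0.975, n-1) x SD / sqrt(n). At n = 15 this is 2.145 / sqrt(15) = 0.554 SD. With fewer patients the factor is 0.635 (n = 12) or 0.715 (n = 10). The documents give no SD for weight change. Over an assumed range, at n = 15:

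| Assumed SD of change (kg) | Half-width (kg) |
|---|---|
| 2 | 1.11 |
| 3 | 1.66 |
| 4 | 2.22 |
| 5 | 2.77 |

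These figures describe the precision of the proposed summary. They do not measure harm from the omission.

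**The case against.** The best defence is that weight is not absent from the report. Baseline weight and BMI are summarised, and a weight-gain event would be counted by preferred term. Individual weights may well appear in the physical examination listing, which for 15 patients can be read by eye. Changes in adipose and muscle volume get a 95% CI. All of this stands. A reader might infer that the trial would report no weight result at all, and the documents do not support that.

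A reader might also infer that the SAP has formally removed weight from the analysis, because SAP section 1 lets differences described there supersede the protocol. That is doubtful. Silence about weight is not clearly a described difference, and the synopsis commitment on safety data covers weight. The SAP is better called incomplete on this point. The one explicit difference concerns physical examination, which protocol 8.2.3 summarises and the SAP only lists, and 8.2.3 does not name weight.

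Finally, the risk should not be overstated. Protocol 2.3 says of agonists with higher PPAR-gamma binding that "side effects such as edema, weight gain, bone effects and cardiovascular complications may occur". It goes on to suggest that a predominantly alpha agent with moderate gamma activity may avoid weight gain, and section 2.2 describes saroglitazar as that type. The support for treating weight gain as relevant here is section 9.4.5, together with the listing of body weight as a safety criterion.

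None of this supplies the missing summary. A listing is not an estimate, event counts depend on reporting, and MRI volumes at two time points are not body weight.

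**Conclusion.** The point holds in this form: the SAP plans no aggregate summary of post-baseline body weight or weight change, for a measure that the protocol names as a separate safety criterion and collects at every visit from Visit 2. Up to 105 post-baseline values are affected, assuming that all 15 patients attend all seven visits. The likely consequence is that a modest shift in weight not recorded as an adverse event would be shown in no table.

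This rests on the text of the two documents. The SAP's study-plan table is not in the text available for review, but a visit schedule would not normally set an analysis. With one arm and standard-of-care management of obesity allowed, a weight-change summary would describe what happened and could not by itself attribute it to the drug. The matter is an improvement available at almost no cost. It does not put the trial's validity in question.

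**What to change.** Add body weight to the safety endpoints in SAP 8.1 and to the summary in SAP 8.3.3. Report observed value, change and percent change from baseline at Weeks 4, 8, 12, 16, 20, 24 and 28 in the safety population, with the statistics already used there for vital signs. SAP 6.1 already defines change and percent change. Name body weight in the corresponding listing as well. Separately, reconcile SAP 8.3.4 with protocol 8.2.3 on whether physical examination is summarised or only listed.

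A 95% CI for change at Week 24 is optional, since the SAP gives vital signs none. A count of patients gaining more than 5% is best left out, or labelled purely descriptive: the 5% in exclusion criterion 7 is a limit on weight change in the 3 months before enrolment and not a safety threshold.

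The cost is one more parameter in an existing table, with no new data, visit or patient. Writing it into the SAP before database lock also avoids a later choice made with the data in view.

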### 8.3.5 Laboratory Results

Clinical laboratory evaluations consist of hematology, clinical biochemistry and urinalysis. Laboratory assessment for the urinalysis, lipid profiles and HbA1c will be performed at Screening, Baseline, Week 12 and Week 24 visits. Laboratory assessments for FSIVGTT and metabolic flexibility assessments will be conducted at Baseline and Week 24 Visits. Laboratory assessments for all other parameters will be performed at screening, baseline and Week 4, 8, 12, 16, 20, 24 and 28 visits. Laboratory values will be presented using the International System of Units (SI units).

Observed and changes from baseline values will be summarized descriptively (N, mean, median, standard deviation, minimum, and maximum values) for all hematology and biochemistry parameters at each assessment. A summary table of the categorical grade shift changes using the normal ranges from baseline to last study visit will be provided.

For summary purposes, laboratory values that are listed as above or below particular thresholds will be numerically listed as above or below that threshold, respectively, by the minimum measured amount for that parameter. For example, if a parameter is measured to

Document Title:	Statistical Analysis Plan		
Version Number:	1.0	Date:	31 Dec 2021
Protocol Number:	SARO.17.010	Sponsor Name:	Zydus Therapeutics Inc.

A listing will be provided which contains data for each laboratory parameter for all enrolled patients.

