Pharmacokinetics of Saroglitazar will be assessed following first dose and last dose in liver transplant recipients with NAFLD. The samples will be collected at Pre-dose (0.0), 0.5, 1.0, 2.0, 3.0, 4.0, 6.0, 8.0, 10.0 and 24 hours post-dose. In addition, pre-dose sample will be collected at Visits 3, 4, 5, 6 and 7.

At the End of Treatment visit, all required parameters and assessments will be performed again.

Subjects will return for their final visit, the Follow-up visit, 4-week after the last dose of the study drug. At this visit assessments include a targeted physical examination (lab results/signs/symptom driven), vital signs, safety laboratory tests, a review of concomitant medications and AEs. A urine pregnancy test will be performed for females of child bearing potential only. All the study related procedures will be performed as per table 1 (Schedule of Events).

Unscheduled visits – Permitted at any time during the study for assessment and management of AEs and any concurrent clinical conditions. To be captured in the electronic case report form (eCRF).

• If further investigations are required in case of any AEs, PI will assess the AE and take necessary action, if required.

Approved by: Protocol No.: SARO.17.010
[name] [name] Version No.: 7.0

Confidential Page 8 of 80

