#### **Unscheduled visits**

Unscheduled visits are permitted at any time during the study at the discretion of the PI or designee for assessment and management of AEs and any concurrent clinical conditions, Data will be captured in the eCRF.

If further investigations are required in case of any AE, PI will assess the AE and take necessary action, as required.

Immunosuppression levels will be monitored on Day -1, Day 1, Day 3, Day 7 and Weekly (Days 14, 21 and 28) for first month. If the Immunosuppression levels remain stable as per the opinion of the transplant hepatologist, they will then be monitored on a monthly basis (Days 57, 85, 113, 141 and 169) until the end of the study or as per the opinion of the transplant hepatologist/study investigator for clinical care.

If due to any reason after randomization, the patient discontinues the study before the End of Study Visit, all procedures of End of Study Visit (Visit 9) should be carried out.

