## 2.2 Study Description

### 2.2.1 Study design

[figure not shown]
This is a Phase 2A prospective, single-center, open-label, single-arm study to evaluate the safety, tolerability and efficacy of Saroglitzazar magnesium 4 mg in liver transplant recipients with non-alcoholic fatty liver disease. Patients who are at least 6 months post-transplant for non-alcoholic steatohepatitis (NASH) or cryptogenic cirrhosis thought to be secondary to NASH are eligible to be enrolled in this study. Approximately 15 male and female patients aged 18 to 75 years who meet the inclusion and exclusion criteria will be enrolled. All eligible patients will receive Saroglitzazar magnesium 4 mg once daily in the morning for a period of 24 weeks.

This study will be conducted over a period of up to 33 weeks and will include a 5-week screening period, a 24-week treatment period and a safety follow-up visit, 4 weeks after the last treatment. The screening period may be extended under special circumstances with the explicit approval of the Sponsors' Medical Expert(s). The study visits will occur at Screening, Baseline (day 1), Week 4 (Day 29 ± 3 days), Week 8 (Day 57 ± 3 days), Week 12 (Day 85 ± 3 days), Week 16 (Day 113 ± 3 days), Week 20 (Day 141 ± 3 days) and Week 24 (Day 169 ± 3 days). A

Document Title:	Statistical Analysis Plan		
Version Number:	1.0	Date:	31 Dec 2021
Protocol Number:	SARO.17.010	Sponsor Name:	Zydus Therapeutics Inc.

[figure not shown]
safety follow-up visit will be conducted approximately 4 weeks after the administration of last dose of the study drug (Day 197 ± 3 days).

Approximately 5 patients will be included in the pharmacokinetic assessment. Pharmacokinetics of Saroglitzazar will be assessed following administration of first (Baseline) and last dose (Week 24). The samples will be collected at Pre-dose (0.0) and 0.5, 1.0, 2.0, 3.0, 4.0, 6.0, 8.0, 10.0 and 24 hours post-dose. In addition, pre-dose sample will be collected at Week 4, 8, 12, 16 and 20 Visits. The study plan is provided below.

Document Title:	Statistical Analysis Plan		
Version Number:	1.0	Date:	31 Dec 2021
Protocol Number:	SARO.17.010	Sponsor Name:	Zydus Therapeutics Inc.

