## 3.1 Efficacy Analysis Populations

The modified intent-to-treat (mITT) population includes all enrolled patients who receive at least one dose of study drug and have at least one post-baseline assessment visit. The mITT population will serve as the primary analysis population for all efficacy analyses. Last observation carried forward (LOCF) method will be used as an imputation method for the efficacy variables with missing observations.

The supportive analysis of the efficacy endpoints will be conducted using per-protocol (PP) population. The PP population includes all enrolled patients who receive at least one dose of study drug, complete the study (Week 24 assessment) in compliance with the protocol and do not have any major protocol violations.

The number of patients excluded from mITT and PP populations and a listing of excluded patients from each analysis population with reason for exclusion will be presented.

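### The SAP's one laboratory shift table ends at an undefined last study visit, so it does not count patients whose values shifted earlier and recovered

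*SAP*

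**What the plan says.** For laboratory results, SAP 8.3.5 plans descriptive statistics of observed values and changes at each assessment, a listing for all enrolled patients, and one categorical table: "A summary table of the categorical grade shift changes using the normal ranges from baseline to last study visit will be provided". The readable SAP does not say which visit that is.

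The sampling times differ by parameter. For most, "Laboratory assessments for all other parameters will be performed at screening, baseline and Week 4, 8, 12, 16, 20, 24 and 28 visits". For three groups, "Laboratory assessment for the urinalysis, lipid profiles and HbA1c will be performed at Screening, Baseline, Week 12 and Week 24 visits".

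Three sets of passages bear on the end visit:

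- **Week 24.** SAP 2.2.1 begins its list with "The study visits will occur at Screening, Baseline (day 1), Week 4" and runs it to Week 24. It then adds, as a separate item, that a "safety follow-up visit will be conducted approximately 4 weeks after the administration of last dose of the study drug". The per-protocol definition in SAP 3.1 requires patients to "complete the study (Week 24 assessment) in compliance with the protocol".
- **Week 28.** The protocol summary, under Study Schedules, states: "Subjects will return for their final visit, the Follow-up visit, 4-week after the last dose of the study drug". For patients who leave early, Protocol 7.2 (Unscheduled visits) says that "all procedures of End of Study Visit (Visit 9) should be carried out".
- **Each patient's own last visit.** SAP 8.3.1 calculates study duration from the date of the last visit, whenever that falls.

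Two other outputs matter here. Protocol 8.2.3 plans frequencies of abnormal laboratory values by visit. SAP 8.3.2 tabulates treatment-emergent adverse events, counting a patient once per preferred term and reporting maximum severity.

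**The concern.** Protocol 6.1.1 makes clinical laboratory tests part of the primary endpoint. The natural safety question is how many patients moved from normal to abnormal at any time after starting drug. A shift table that ends at one late visit answers a different question: how many are abnormal at the end. If the end is Week 28, completers have by then been off drug for four weeks.

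The protocol's own follow-up rule pulls the two answers apart. Under Protocol 5.9.1, a patient who meets a laboratory discontinuation criterion is followed until values are back to baseline or stable. The last value can therefore be the recovered one, and the table can show no shift for a patient who stopped drug because of a shift. Because the visit is not named, two programmers could also build different tables from the same sentence.

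**Working it through.** The plan gives no figure to reproduce. The check is which values each reading can use, and whether another planned output supplies the missing count.

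**Step 1: assessments available (SAP 8.3.5).** Parameters sampled at every visit have on-treatment assessments at Weeks 4, 8, 12, 16, 20 and 24, which is 6, plus Week 28 off treatment. Urinalysis, lipids and HbA1c have Weeks 12 and 24, which is 2, and no Week 28 sample.

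**Step 2: what the shift table uses for a patient who completes.**

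| Reading | Sampled at every visit | Urinalysis, lipids, HbA1c |
|---|---|---|
| Week 24 | 1 of 6 on-treatment values | 1 of 2 |
| Week 28 | 0 of 6 (off-treatment value) | no sample at that visit |
| Own last visit | same as Week 28 for a completer | no sample at that visit, unless last available value is meant |

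**Step 3: follow two hypothetical patients.**

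- *Patient A* has normal ALT at baseline, values above normal at Weeks 8 and 12, and normal values from Week 16. All three readings give normal to normal.
- *Patient B* has normal lipase at baseline and exceeds the upper limit of normal at Week 8. This is a discontinuation criterion in Protocol 5.9.1. The patient is stopped and followed until the value is normal, then leaves the study with Visit 9 procedures. The own-last-visit reading gives normal to normal, as does the Week 28 reading if Visit 9 stands in for Week 28. On the Week 24 reading there is no value to tabulate. No reading counts a shift.

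**Step 4: can another planned output supply the count?**

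- *By-visit abnormality frequencies (Protocol 8.2.3).* These stand, because SAP 1 overrides the protocol only where the SAP describes a difference, and it describes none here. They do not relate a value to that patient's baseline or link patients across visits. Protocol 4.3 excludes only ALT above 3 times the upper limit of normal, so ALT can be abnormal at entry. One patient abnormal at baseline and at all six on-treatment visits gives a count of one each time, with zero shifts from normal. The same counts arise if that patient normalises by Week 4 and another patient, normal at baseline, is abnormal at all six visits: one shift.
- *By-visit minimum and maximum.* These can show that a limit was crossed, but not by how many patients or from what baseline category.
- *Adverse event tables (SAP 8.3.2).* These count patients. Under Protocol 6.2.10, a result that leads to discontinuation meets a reporting criterion, but a documented justification for not reporting is allowed. Protocol 9.4.1 leaves clinical significance to the investigator's judgement. Baseline category is not shown.
- *Listing.* It allows a hand count across 15 patients, but it is not a table.

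**The case against.** The strongest reply is that a baseline-to-one-visit shift table is meant to use one value per patient, and that the other outputs cover the rest. Every visit is summarised, abnormal frequencies by visit are planned, and 15 patients can be read from a listing. The crossings that matter most clinically should reach the adverse event tables, where patients are counted. On this view, only transient excursions that met no reporting criterion remain, and a worst-value table for an exploratory single-arm study is a preference. Much of this stands, and it is why the point is minor. It does not supply the count of distinct patients who shifted, and it does not name the end visit.

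Four stronger readings are tempting, and the documents do not support them:

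- *Five of six on-treatment values, or all six, are lost.* They are not. They do not enter this one table, but they are summarised and listed.
- *By-visit counts at least bound the number of patients who shifted.* They bound patients with an abnormal value. Because baseline ALT may be abnormal, shifts from normal can be zero even when every visit shows an abnormal count.
- *A Week 28 end point conflicts with the treatment-emergent basis of SAP 8.* It does not. The adverse event period in SAP 8.3.2 runs to study exit, so Week 28 lies inside it.
- *The end visit must be either Week 24 or Week 28.* SAP 8.3.1 makes each patient's own last visit a third possibility.

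**Conclusion.** The concern holds as a minor, cheaply corrected reporting gap in a primary-endpoint safety output. The end visit is undefined in the readable SAP. The protocol's terms favour Week 28, but neither protocol passage refers to the shift table. On all three readings, a value that shifted earlier and returned to normal is not counted, and no stated table gives the number of distinct patients who shifted from baseline.

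The documents give no expected rate of transient shifts, so the number of patients affected cannot be estimated.

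The conclusion rests on the readable text. SAP 8.3.5 breaks off mid-sentence after the shift-table sentence, and the visit schedules in Protocol section 1 and SAP 2.2.2 could not be read. A label there might name the visit. That would settle the ambiguity, but a single end visit would still miss recovered shifts.

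**What to change.** Replace the shift-table sentence in SAP 8.3.5 with the following:

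*Shift tables using the normal ranges will be provided from baseline to (a) the worst post-baseline value, scheduled or unscheduled, from first dose to study exit (the treatment-emergent period of Section 8.3.2), with highest and lowest shown separately and values after the last dose flagged; and (b) Week 24/EOT, or the last value on or before the last dose for early discontinuers. Week 28 values will be shown separately as off-treatment.*

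Running the window in (a) to study exit keeps a peak found on repeat testing just after drug is stopped. The flag keeps on-drug and off-drug values distinguishable.

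The cost is about three extra displays: worst high, worst low, Week 24/EOT and off-treatment, in place of one table. No new samples, visits or patients are needed. One caution for interpretation is that the worst of several values crosses a limit by chance more often than a single value does, and there is no control arm to calibrate this. Table (b) should therefore be read beside table (a).
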